## Selection criteria

A series of criteria are established to select or reject patients.

#### **Inclusion Criteria:**

- Age ≥ 18: To ensure that participants are adults and consent in an informed manner.
- **Indication for diagnostic hysteroscopy** in the office: The patient must be scheduled for a diagnostic hysteroscopy procedure, either for evaluation of the uterine cavity or diagnosis of pathologies.
- Simple procedures or **polypectomies of 1, 2 or more than 3 polyps.** Patients requiring uterine polypectomies of different sizes (1, 2 or more than 3 polyps) will be included, which will allow the response to pain to be compared depending on the extent of the intervention.
- or Realization of **biopsy**: Patients who need an endometrial biopsy during the Hysteroscopy also Be Including.

These two variables account for the vast majority of procedures performed in the clinic.

• **Not having performed previous hysteroscopies**: To minimize the bias derived from familiarity with the procedure and its sensations, patients who have had a previous hysteroscopy will be excluded. This will help to assess pain in a more *naïve population* with respect to technique.

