#### Possible limitations

The anesthesia used in this study involves the administration of injections into the uterosacral ligaments, which makes masking difficult for the patient, as she is likely to be aware of such an intervention. A double-blind design is not possible, as the doctor administering the anaesthesia knows whether or not he is administering it. In addition, in a single-blind placebo design (such as saline), there may be difficulties in masking the procedure, as the simple sensation of the injection could influence the patient's perception of pain. Therefore, irrigation of the vagina and cervix with saline solution of saline solution will be proposed, simulating the application of local anesthesia, without injecting it.

The fact that the study does not employ a blinded design, either for the patient or for the physician, introduces certain limitations and potential biases. However, some of these biases are controllable and can be minimized with specific measures. For all these reasons, biases associated with the lack of masking can be incurred. These biases that need to be addressed are the ones mentioned below

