#### Procedure variables

- **Physician who performs the test** (Type of variable: Nominal qualitative) The professional who carries out the procedure.
- **Degree of experience of the physician** (Type of variable: Ordinal qualitative):
  - o Low: 5-20 procedures performed.
  - o Normal: 20-50 procedures performed.
  - o Discharge: >50 procedures performed.
- **Test Duration** (Variable Type: Continuous Quantitative) The total time of the procedure, which could correlate with the pain experienced.
- Use of the outer sheath (return) (Dichotomous qualitative: Yes/No)
- **Bipolar energy use** (Variable type: Qualitative dichotomous) Yes/No. The use of bipolar energy could influence pain due to the impact on the tissues.
- Number of polyps removed (Variable Type: Discrete Quantitative) 1, 2 or
- >2. The number of polyps could affect the level of pain due to time and additional manipulation.
- Number of biopsies taken (Variable Type: Discrete Quantitative) 1, 2 or
- >2. More biopsies may increase discomfort during and after the procedure.
- **Type of endometrial pattern** (Type of variable: Nominal qualitative) Atrophy, proliferative, menstrual or secretory. Different endometrial patterns can influence pain perception.
- **Number of Cavity Entries** (Variable Type: Discrete Quantitative) The number of times the hysteroscope needs to be inserted into the uterine cavity may be influence in the pain.
- **Insertion technique** (Variable type: Nominal qualitative) Direct entry vs. with speculum and forceps. Insertion techniques could have different implications on perceived pain.

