## 1. Equipment Used

- Ultrasound with transvaginal probe: To evaluate the patient's anatomy before the test and detect possible post-procedure complications.
- Hysteroscope: A 5 mm 30° Betochi diagnostic hysteroscope will be used. If the return pod applies, it must be specified.
- Distension medium: 0.9% saline solution will be used to ensure adequate visualization during the intervention.
- Irrigation pressure: It will be maintained between 100-120 mmHg to ensure correct distension of the uterine cavity without compromising patient safety.

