#### 3.3. Post-Injection Monitoring

- At least 1 minute after injection should be allowed before starting hysteroscopy to ensure the effect of the anaesthetic.
- In case of persistent severe pain, additional measures may be considered, such as a new administration of anesthetic or complementary sedation, if indicated and approved.

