## **Step 6: Resolution of Benign Pathology (if applicable)**

If polyps or other benign lesions are identified, the following shall be done:

- Polypectomy: Versapoint forceps (bipolar system) or flexible scissors will be used for polyp removal.
- Biopsies: Endometrial samples will be obtained with the most appropriate technique to minimize discomfort.

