**Parity** 

Type of pathology treated

Other relevant factors

This analysis will allow us to identify possible subgroups with significant differences in the results.

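### The subgroup factor for pathology treated is settled only after randomisation and anaesthesia, so comparing the arms within it would not be a randomised comparison

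*Protocol*

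**What the plan says.** - **Inclusion Criteria.** Simple procedures, biopsies and polypectomies of varying number are admitted, "which will allow the response to pain to be compared depending on the extent of the intervention". This is a reason given inside a criterion. Objectives of the study does not list it.
- **3.2. Analysis by Subgroups.** The factors are age, parity, "Type of pathology treated" and an open category of other factors. The stated use is: "This analysis will allow us to identify possible subgroups with significant differences in the results".
- **Procedure variables.** Extent is recorded as what was done, for example "Number of polyps removed" and the number of biopsies. None of the variable lists contains a polyp status known before allocation.
- **Order of events.** Randomization process places allocation before the procedure. The injection is Step 1, and "At least 1 minute after injection should be allowed before starting hysteroscopy". Treatment of lesions comes at Step 6: "If polyps or other benign lesions are identified, the following shall be done".
- **Knowledge of the arm.** Possible limitations says "the doctor administering the anaesthesia knows whether or not he is administering it", and the Protocol compliance limitation says that the trial is run without blinding. Consent collection in hysteroscopy consultation does call the trial blinded, but that passage concerns what the patient is told.
- **Pain and the procedure.** The Introduction names pain among the main reasons for failure. Justification of the relevance of the study says that some women need sedation in the operating room because of pain. Variables of post-procedure pain records surgical referral due to pain.

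**The concern.** Age and parity are fixed before allocation, so anaesthesia and control can be compared within them with randomisation intact. The pathology treated is different: it is a result of the procedure and can depend on how much the woman tolerates. Tolerance depends on pain, which is both the outcome and what the anaesthetic is meant to change.

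If a woman with a polyp cannot tolerate its removal and is then counted as not treated for a polyp, women with the same disease are sorted differently in the two arms. If anaesthesia works, this happens more often among controls. The treated control group then loses its most painful cases and the untreated control group gains them. The apparent benefit shrinks among treated women and grows among the rest, even when the true effect is the same in both. A reader of the trial could conclude that anaesthesia helps less when polyps are removed.

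**Working it through.** **Inputs from the protocol.** Expected difference 1.5 VAS points, SD 2.0, alpha 0.05 (two-sided assumed, as sidedness is not stated), power 80%, 29 per group.

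**The plan's own figure.** Effect size 1.5 / 2.0 = 0.75. A two-sample t-test needs 28.90 per group, rounded up to 29, with power 0.801. The 29 reproduces, and this point does not change it.

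**Order of events.** Allocation → injection or irrigation → wait → access → inspection → treatment at Step 6. The factor is therefore a post-randomisation variable. This needs no arithmetic.

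**Illustration 1 (assumptions, not from the documents).** VAS = 4 + U − 1.5·A + e, with SD of U 1.5 and of e 1.3, so total SD = √(2.25 + 1.69) = 1.98. A is 1 with anaesthesia. Half of the women have a polyp, and removal adds 0.5 point. The polyp is left if pain reaches a limit. Benefit is control minus anaesthesia:

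| Rule for leaving the polyp | Treated | Untreated | Gap |
|---|---|---|---|
| Final VAS at or above 6 | 1.11 | 1.75 | 0.64 |
| Final VAS at or above 7 | 1.29 | 1.68 | 0.39 |
| Separate pain reading at or above 6 | 1.27 | 1.64 | 0.37 |
| Separate reading at or above 6, only 30% of these stopped | 1.45 | 1.56 | 0.11 |
| Every polyp found is removed | 1.50 | 1.50 | 0 |

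Grouping by polyp present gives 1.44 in the first row. That is a fair randomised estimate. About 16% of control and 4% of anaesthesia polypectomies are abandoned, so the extra removals under anaesthesia add 0.5 × (0.16 − 0.04) = 0.06 point, and 1.50 − 0.06 = 1.44.

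**Illustration 2 (assumptions).** Control mean 5, SD 2.0, no added pain from removal. Removal depends on access pain, which correlates 0.3 to 0.7 with final pain, with limits of 8, 7 or 6. Grouping by polyp present returns 1.50. Grouping by polyp treated gives 1.07 to 1.44 in the treated and 1.56 to 1.67 in the untreated. With no pain limit, both groupings give 1.50.

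**Against sampling noise.** With 58 patients split evenly into two subgroups there are 14.5 per arm in each. The standard error of one subgroup effect is √(2 × 2.0² / 14.5) = 0.74. For the difference between two it is √2 × 0.74 = 1.05. Power for 1.5 points within one such subgroup is about 50%.

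**The case against.** The strongest reply is that the text does not clearly plan the analysis at issue. The inclusion rationale, and the opening of section 3.2 on factors that influence variability of pain, can be read as asking how pain varies with what was done. For that question the extent actually performed is the right variable. This stands, and it limits the point to comparisons of the arms. The other reading remains open, however, because the aim of finding subgroups with differing results is not confined to prognosis.

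A reader might also infer four stronger things, which the documents do not support:
- **That comparison by extent is a trial objective.** Objectives of the study does not list it.
- **That women whose removal is stopped are moved to a diagnostic subgroup.** This is inference. Section 3.1 excludes incomplete data, so they might be dropped, which would be a different problem. Step 6 also directs that lesions found be treated, which narrows discretion, though it does not exclude stopping for pain.
- **That the hysteroscopist is shown to know the arm.** Possible limitations speaks of the doctor who injects. That this is the same person is implied, not stated.
- **That the bias is known to be large.** The 1.11 and 1.75 come from selecting on the outcome itself and abandoning every case over the limit. The documents give neither a stopping rate nor a polyp prevalence.

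It is also true that the largest illustrated gap, 0.64, is below its standard error of 1.05. That makes a false finding from this source alone less likely. It does not make the contrast valid, since the error runs in one direction.

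**Conclusion.** The point holds in conditional form. Section 3.2 names a subgroup factor that is settled after randomisation and after anaesthesia, in an unblinded setting, and the protocol itself says that pain can stop or divert the procedure. If the arms are compared within it, the contrasts are not randomised comparisons and can show a spurious difference in effect.

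The size cannot be derived from the documents. With a true effect of 1.5 in everyone, the illustrated gap between untreated and treated women runs from 0.64 under strong selection, through 0.11 when few procedures are stopped, to zero if every polyp found is removed. In both models, whenever removal depends on pain, the benefit is understated among treated women. The primary comparison of all patients is not affected by this point, nor is the sample size.

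**What to change.** In section 3.2, for any comparison of the treatment effect, replace the pathology-treated factor with the indication or suspected pathology (no focal lesion / suspected polyp), recorded at the indication visit before the draw. Use an ultrasound finding only if it is already available then. Equipment Used lists ultrasound "To evaluate the patient's anatomy before the test", which does not show that a result exists at allocation.

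Keep pathology treated, polyps removed and biopsies taken as descriptive results by arm, or as descriptors of how pain varies with the procedure. State that they are not subgroup factors for the treatment effect, and align the rationale in Inclusion Criteria with this.

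The cost is one item in the data sheet and a changed definition, with no extra patients. The downside is a somewhat less sharp subgroup, because suspected pathology will not always match the hysteroscopic finding. Being fixed before allocation, that mismatch cannot be influenced by the arm.

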#### **Exclusion Criteria:**

- **Age < 18 years:** Underage patients will not be included, as valid and adequate informed consent cannot be obtained.
- **Known allergy to some type of local anesthetic**: Patients with a history of allergies or serious adverse reactions to local anesthetics will be excluded to avoid risks related to drug administration.
- General contraindications to hysteroscopy: Pregnancy (the status of 'non-pregnancy' is established in a surrogate manner by the interview with the patient and according to her FUR, menstrual frequency or sexual intercourse in the last month or objectively by prescribing ACHO from the indication of the test or performing a pregnancy test before it), active infection (pyometra or history of recent pelvic inflammatory disease or suggestive symptoms), recent uterine perforation, etc.

## Complex procedures:

- Morcellator myomectomies: More complex surgical procedures, such as morcellator myomectomy, are excluded because of their level of invasion and difficulty, which could interfere with the isolated assessment of anesthesia-associated pain.
- Failure to access the uterine cavity: If adequate access to the uterine cavity is not achieved, the procedure is considered incomplete and the patient will be excluded from the study.
- Situations that prevent access to the cavity: Patients in whom hysteroscopy is failed, with cervical stenosis or other anatomical defects that completely prevent adequate access to the uterine cavity will be excluded.
- Long interventions with a large fluid passage or water balance above 1000 cc: In these cases the patient may experience additional pain due to other circumstances unrelated to the routine procedure.
- **Known uterine malformations**: Patients with uterine malformations (such as septate, unicornuate, or bicornuate uterus) will be excluded, as this could complicate access and interpretation of results, as well as affect pain tolerance during hysteroscopy.
- Waiting times longer than 60 minutes: It has been associated with an increase in pain according to the SEGO guideline for ambulatory hysteroscopy.
   Taking analgesic medication before the test: Taking medication before the test may alter the results.
- Major complication associated with the intervention: Uterine perforation, creation of false pathway or false endocervical pathway or intense bleeding (expressed as hemorrhage that requires additional maneuvers than usual for resolution).
- Failure to provide adequate informed consent in consultation or the anxiety assessment scale prior to the procedure.

#### Justification of the Criteria

- **1. Age and informed consent:** Ensures that all participants are adults and capable of providing informed consent in a conscious and voluntary manner.
- **2. Indications for hysteroscopy**: By selecting patients with relatively common diagnostic and therapeutic indications, it is ensured that the study is representative of the general population undergoing this procedure.
- **3. Absence of prior hysteroscopies**: Excluding patients with previous experience minimizes biases related to advance knowledge of the test and its possible painful sensations.
- **4. Complex procedures and uterine malformations**: Excluding cases of high complexity or anatomical complications allows the study to focus on routine diagnostic procedures with less variability in terms of technique and pain tolerance.
- **5.** Taking medication before the test or taking chronic pain medication: Taking medication can alter the results.

With these well-established inclusion and exclusion criteria, it is ensured that the study focuses on a homogeneous population, with a controlled level of risk and without factors that may excessively interfere with pain measurement and the effectiveness of local anesthesia. These criteria also help to improve the internal validity of the study, minimising potential biases that could affect the results.

## Explanation of Proof and Delivery of Informed Consent

Informed consent is a crucial component of ensuring that participants understand the procedures, risks, and benefits of participating in the study. The detailed procedure for the delivery and explanation of informed consent in the context of this study is described below.

## **Delivery of Informed Consent:**

Aspects Legal and

Ethical

In accordance with current legal regulations, informed consent must be provided in writing, guaranteeing that the patient has understood all the implications of the study and has voluntarily given her consent to participate.

It is important for the patient to know that she will be able to withdraw at any time during the study without affecting her medical care or future treatment.

## **Summary of the Consent Delivery Procedure:**

- 1. Delivery and signature of the informed consent at the time of indication of the hysteroscopy.
- **2.** Explanation of the study and requirement of your signature for inclusion in the study, if the patient agrees to participate.
- **3.** Simple 1:1 randomization of patients using the random system proposed in the protocol. The patient's CH should be noted for the group to which she belongs.
- **4.** Explanation of the procedure again on the day of the intervention, ensuring that it is not mentioned if anesthesia will be used to avoid bias in the evaluation of pain.
- **5.** Collection of the signed consent in consultation, before the intervention, to confirm participation

This procedure ensures that all ethical and legal regulations are complied with, and that the study is conducted in a controlled manner, with minimal risk of bias, ensuring data integrity and the well-being of participating patients.

## Time of delivery:

The informed consent will be given to the patient at the time when the diagnostic hysteroscopy is indicated, that is, when it is decided that the patient will undergo this procedure in consultation.

The patient will receive written consent and will be given the necessary time to read it carefully, resolve any doubts with the medical staff and reflect on her participation in the study.

It will also be explained that the signing of consent is a prerequisite for the procedure and that participation in the study is voluntary, and can be withdrawn at any time without affecting your medical treatment.

#### **Content of informed consent:**

Informed consent should detail all relevant aspects of the study, including:

- The standard procedure for diagnostic hysteroscopy.
   Possible risks and benefits of the intervention.
- Description of the local anaesthesia to be administered in the relevant group, and the option of no anaesthesia in the control group and a placebo instead. It is important to mention this because the patient who does not receive anesthesia must wait for an intervention, otherwise, she could know that nothing is being administered.
- Confidentiality of the data and the conditions under which they will be used.
- Information about randomization in the study (whether or not anesthesia will be used), and that this decision will be made randomly.
- Delivery of the **STAI** (**State-Trait Anxiety Inventory**) **questionnaire**, which the patient must complete before the procedure.

As an important note: The professional in charge of delivering the information should try to influence the patient's expectations as little as possible, transmitting the information clearly, but avoiding both minimizing her possible fears and inducing them unnecessarily. That is, when explaining the procedure and the objective of the trial, it should be emphasized that there is no solid evidence that anesthesia is useful in this procedure and that, in fact, its use is not routinely standardized and that in many patients it is not administered. In addition, it will be emphasized that the objective is to demonstrate whether this practice, which can also be uncomfortable for the patient, could be avoided. They should be reassured, resolve their doubts and explain that most patients tolerate this procedure without anesthesia, however, they should not dwell too much on this aspect to minimize knowledge bias, since many patients forget irrelevant information when the day of the intervention arrives. In this way, the inherent fear that any patient has of a procedure that is painful before it is partially counteracted.

## **Consent collection in hysteroscopy consultation:**

On the day of the intervention, the patient will deliver the signed informed consent, which was previously provided and explained.

The explanation of the procedure will be reiterated, including details about what will occur during the diagnostic hysteroscopy, but without mentioning whether or not anesthesia will be used. This is essential to avoid biases in the perception of pain, which could be influenced by prior knowledge of the intervention.

It will be ensured that the patient understands that consent has already been provided and that this is an additional step in the information process. The patient will be able to ask questions or express any concerns at this time.

If the patient asks if she will be given anesthesia, as it is a blinded trial, it is included in the document of the patient's participation in the trial, that the doctor may refrain from communicating to her which treatment group she is in, therefore, it is especially important that this group is hidden. However, again, an attempt will be made to reassure the patient, explaining that the procedure is usually well tolerated with and without anesthesia and that, in addition, routinely, the use of anesthesia may or may not be applied equally according to the criteria of the doctor performing the test, as there is no firm recommendation on its use. To further minimize bias, all patients will be fitted with the speculum to perform a correct vaginal and cervical examination and will be irrigated with saline solution in the control group as explained in the protocol.

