#### **Observer Bias:**

If the doctor in charge of assessing pain knows the group to which the patient belongs (anesthesia or non-anesthesia), he could subtly influence how he collects the data (for example, by showing greater empathy or being less rigorous in control).

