## **Protocol compliance:**

Although participants and practitioners will be instructed on the study protocol, there may be variability in adherence to the study, especially in data collection or implementation of interventions, which could introduce additional biases.

Given the above, it has been decided to carry out the clinical trial without blinding. However, strict variables that may influence the perception of pain should be established and should be carefully collected and controlled during the study to minimize biases as much as possible.

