## Minimization of Biases by Prior Knowledge of the Intervention:

The process described also helps to minimize biases that could arise due to the expectation or advance knowledge about the application of anesthesia. Even if the patient has previously signed the informed consent, it is important to consider that a high percentage of patients do not read the entire content of the consent in detail or do not remember all the aspects mentioned, especially the part referring to anesthesia. This simulates a masking in the study, in which the patient does not know if she will be given anesthesia, which allows the perception of pain to be more objectively assessed without the expectation of treatment influencing her experience.

Even if the test has been verbally explained in the consultation, the patient may not remember all the details related to anesthesia on the day of the intervention. This approach ensures that the perception of pain in each group (with or without anesthesia) is not affected by the patient's mental or emotional predisposition to know the treatment in advance. Therefore, biases related to expectation are reduced, which improves the quality of the data obtained.

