## 2. Hysteroscopy

The procedure will be carried out following a series of standardized steps to ensure its effectiveness and safety.

As a previous step, **in the control group**, the speculum will be placed to assess the vagina and cervix and the vagina and cervix will be irrigated with a syringe, using 0.9% saline solution, up to 4 times, in the same way as if we applied the local anaesthetic.

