## **Step 2: Entry by Vaginoscopy**

The procedure will be initiated by vaginoscopy, ensuring clear visual access to the intervention area.

The insertion of the hysteroscope into the cervical canal will be performed at least 1 minute after the application of the local anesthesia.

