#### **Informed Consent**

- All participants will sign an **informed consent document** before their inclusion, which will detail:
  - o Objectives, procedures, risks and benefits of the study. o Right to withdraw at any time without penalty. o Randomization and partial masking process (to minimize expectation biases).
  - o Data protection measures and anonymization.
- It is guaranteed that the information will be provided in clear and accessible language, with an opportunity to resolve doubts.

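### The protocol gives conflicting masking statuses and says patient expectation is kept out of the pain score, which a needle-free control and a VAS with no masked assessor cannot deliver

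*Protocol*

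**What the plan says.** The protocol describes masking in five places, and they do not agree:

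- *Possible limitations*: "The fact that the study does not employ a blinded design, either for the patient or for the physician" is given as a source of bias.
- *Protocol compliance*: "it has been decided to carry out the clinical trial without blinding".
- *Consent collection in hysteroscopy consultation*: "If the patient asks if she will be given anesthesia, as it is a blinded trial", the doctor may withhold the group.
- *Informed Consent* (ethics annex): the consent document will explain the "Randomization and partial masking process (to minimize expectation biases").
- *Specific Considerations* (ethics annex): blinding is called not complete, and saline irrigation is offered as mitigation.

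On expectation, *Minimization of Biases by Prior Knowledge of the Intervention* says "This approach ensures that the perception of pain in each group (with or without anesthesia) is not affected" by the patient's predisposition to know her treatment in advance. It also says that pain is assessed without treatment expectation acting on her experience. The same section closes more mildly, with expectation biases being reduced.

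On assessment, *Observer Bias* sets out the risk: "If the doctor in charge of assessing pain knows the group to which the patient belongs", the way the data are collected could change. *4. Data Monitoring and Logging* says a VAS will be obtained without saying by whom. *1. Data Collection* mentions only data collection personnel.

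**The concern.** The primary endpoint is a pain score that the patient reports, so it is open to what she believes she received and to how she is asked. A reader who meets the word blinded, together with a statement that expectation does not act on the score, will take any difference between arms as the effect of the anaesthetic. If the patient can tell her arm, the difference is the anaesthetic effect plus any effect of expectation and of the person asking. The inconsistency also affects conduct: the blinded label is the stated reason for not telling the patient her group, while two other sections say there is no blinding to protect.

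**Working it through.** **Masking status.** *Possible limitations* and *Protocol compliance* say there is no blinding. *Consent collection in hysteroscopy consultation* says the trial is blinded. All of this is current text, and the statements cannot all be true. The two annex statements lie in between and come closest to what the procedures describe.

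**What the patient can perceive.**

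| Element | Anaesthesia arm | Control arm |
|---|---|---|
| Pre-procedure step | Needle injection into both uterosacral ligaments (*3.2. Anesthesia Injection*) | Speculum and syringe irrigation with saline, up to 4 times, no needle (*2. Hysteroscopy*; *Possible limitations*) |
| Interval before insertion | "at least 1 minute after the application of the local anesthesia" (*Step 2*; also *3.3. Post-Injection Monitoring*) | None stated |

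The control step is said to be done "in the same way as if we applied the local anaesthetic", but the written steps differ in the needle. *Possible limitations* concedes that the patient is likely to be aware of the injections, and *Expectation Bias* lists the resulting bias in both arms. *Content of informed consent* requires both the anaesthetic and the placebo alternative to be described to her. Forgetting the consent text, on which the minimization section partly relies, cannot hide what she feels during the procedure.

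**Who could influence the score.** The assessor is not named. Neither a masked assessor nor self-completion is required. The group is written in the Clinical Judgment (*Randomization Method*, *Randomization process*). *3.4. Masking of the Principal Investigator and the Statistician* covers those two roles only, and masking at analysis cannot undo an influence on the score when it was given.

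**Illustration of size.** The plan's own figure first: difference 1.5, SD 2.0 (*Clinically Relevant Difference*), alpha 0.05 and power 0.80. The number of sides is not stated; two-sided is assumed.

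- d = 1.5 / 2.0 = 0.75. The two-sample t-test needs n = 28.9, so 29 per group, as the plan states. Power at 29 is 80.1%.

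Now set the true effect to zero and let reporting shift the arms apart by b points.

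- Standard error = 2.0 × √(2/29) = 0.525; df = 2 × 29 − 2 = 56; critical t = 2.003; noncentrality = b / 0.525.
- b = 0.25: noncentrality 0.476, rejection 7.5%.
- b = 0.5: noncentrality 0.952, rejection 15.5%.
- b = 0.9: noncentrality 1.714, rejection 39.1%.

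The range for b is an assumption: 50% to 90% of patients recognise their arm, and recognition moves the contrast by 0.5 to 1.0 points. That gives 0.5 × 0.5 = 0.25 and 0.9 × 1.0 = 0.9, or 0.25/1.5 = 17% and 0.9/1.5 = 60% of the target difference.

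The shift could also run against the anaesthetic, because the protocol says the injection may itself be uncomfortable. With a true effect of 1.5, the same shifts would leave 1.25 or 0.6 points (noncentrality 2.380 or 1.142), and power would fall from 80% to about 65% or 20%.

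**The case against.** The strongest reply is that most of this is disclosed. *Possible limitations* explains why a saline injection was not chosen, the bias sections name the risks, and four of the five masking statements say that the trial is not fully blinded. The too-strong sentence concerns advance knowledge only, and its section opens and closes with milder wording. The process also includes more than forgetting: a speculum for all patients, saline irrigation, neutral framing and withholding of the group. All of this is accurate. It narrows the point to one label and one claim, but does not remove it: the sections that admit the bias are followed by sections that use the blinded label and claim the bias away.

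Four stronger readings are tempting and are not supported:

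- *The operator collects the VAS.* No section says so. *Observer Bias* is conditional, and the data collection sections name nobody. What can be said is that no masked assessor is specified.
- *The protocol holds throughout that expectation cannot act on pain.* It does not; it lists expectation bias as a limitation.
- *Staff must refuse to tell the patient.* The text says only that the doctor may refrain.
- *The one-minute wait contradicts the control procedure.* The control section states no interval, so there is a gap rather than a contradiction. As a cue it is minor beside the needle, particularly for patients with no previous hysteroscopy.

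It is also fair to object that the size of the bias rests on no figure in the documents.

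**Conclusion.** The point holds in this form. The masking statements conflict, and the statement that pain perception is unaffected goes beyond what the design can deliver and against the protocol's own limitations section. The VAS has no stated protection from an assessor who knows the group. This should be corrected before the trial is reported, because it determines whether a difference can be attributed to the anaesthetic alone.

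The conclusion rests on the text, not on the rejection rates. Those are correct arithmetic under an assumed one-way shift of 0.25 to 0.9 points, SD 2.0, 29 per arm and a two-sided test. They show sensitivity; they do not estimate the bias, whose size and direction are unknown. The lack of a matched control is an acknowledged limitation with a stated reason and is not in itself the error.

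**What to change.** 1. Use one masking description in *Possible limitations*, *Protocol compliance*, *Consent collection in hysteroscopy consultation*, the minimization section and the ethics annex: operator not masked, patient partially masked, analyst masked. In the minimization section, say that the measures may reduce expectation bias in place of the claim that they ensure its absence, and revise in the same way the sentence about assessing pain without expectation. State that the between-arm difference may include expectation effects.

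2. Have the patient mark the VAS herself, out of the operator's view and before any talk of allocation. The cost is a paper form.

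3. Optional: after the VAS, ask which group she thinks she was in and report the answers by arm, descriptively only. A guess made after the pain score is confounded with efficacy, since a patient with little pain may guess anaesthesia, so it cannot separate unmasking from drug effect.

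4. Minor: reconcile *2. Hysteroscopy* with *3.3. Post-Injection Monitoring* and *Step 2*, so that the protocol says whether the interval before insertion applies to both arms.

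None of this changes the drug, the sample size or the primary test, and no extra staff are needed.
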